Arterial Stiffness				X		

RISKS AND DISCOMFORTS:

1. Heart Rate, Arterial Stiffness and Blood Pressure: These are non-invasive procedures that involve minimal risk; however some subjects may experience discomfort when the ECG electrodes are removed from the skin and when the blood pressure cuffs are inflated.
2. Blood Draws: Subject may experience some discomfort when the needle is being place in the arm vein. Expected risks may include bruise or infection at the site of skin puncture, temporary faintness and rarely temporary loss of consciousness.
3. Tilt table: Subjects may feel dizzy, lightheaded or nauseous letting the staff passively reposition the subject from lying down to 30, 45 and 60-degree tilt. A staff member will be supporting the subject during this tilt, but if he or she feels uncomfortable, the staff will stop the test at any time.

DATA ANALYSIS:

Aim 1: To investigate the influence of orthostatic change in BP on plasma renin responses to HUT.

Hypothesis 1A: There will be an inverse relationship between the change in BP and change in plasma renin from supine rest to 60° HUT in individuals with high-level SCI.

Hypothesis 1B: There will be no relationship between the change in BP and change in plasma renin from supine rest to 60° HUT in persons with low-level SCI and uninjured controls.

Orthostatic Blood Pressure and Arterial Stiffness in Persons with Spinal Cord Injury: The Effect of the Renin-Angiotensin-Aldosterone System

Statistical Analysis: To determine the relationship between change in BP and change in plasma rennin, we will use Pearson's correlation coefficient or Spearman's correlation coefficient with alpha. The independent variable is change in SBP from supine rest to 60° HUT and the dependent variable is change in renin from supine rest to 60° HUT. The alpha level will be set at 0.05.

Aim 2: *To investigate the influence of orthostatic change in BP and NE on the RAAS responses to HUT.*

Hypothesis 2A: There will be a linear relationship between the change in orthostatic BP and change in plasma NE concentration from supine rest to 60° HUT.

Hypothesis 2B: Plasma renin activity will be inversely related to plasma NE concentrations during HUT in persons with SCI.

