Statistical Analysis: To determine the relationship between change in BP and NE, we will use Pearson's correlation coefficient or Spearman's correlation coefficient with alpha. The independent variable is change in SBP from supine rest to 60° HUT and the dependent variable is change in NE from supine rest to 60° HUT. The alpha level will be set at 0.05.

Aim 3: *To determine if increased reliance on the RAAS for orthostatic BP regulation contributes to differences in supine AS.*

Hypothesis 3A: There will be significant group differences for change in plasma renin during HUT, in that plasma renin will be significantly increased during HUT in participants with high-level SCI, but will remain unchanged in individuals with low-level SCI and uninjured controls.

Statistical Analysis: Differences in change in plasma renin during HUT between groups will be analyzed using univariate group by ANOVA, with the interaction effect being the statistical effect of interest. The alpha level will be set at 0.05. The G*Power calculations indicate that with a total sample size of 33, there will be a power = 0.8.13 to detect the effect size.

Hypothesis 3B: Change in plasma renin during the HUT maneuver will be directly associated with supine PWV in individuals with high-level SCI.

Hypothesis 3C: There will be no relationship between the change in plasma renin during the HUT maneuver and supine PWV in persons with low-level SCI and uninjured controls.

Statistical Analysis: To determine the relationship between change in plasma renin and supine PWV, we will use Pearson's correlation coefficient or Spearman's correlation coefficient with alpha. The independent variable is change in renin from supine rest to 60° HUT and the dependent variable is PWV during supine rest. The alpha level will be set at 0.05.

Orthostatic Blood Pressure and Arterial Stiffness in Persons with Spinal Cord Injury: The Effect of the Renin-Angiotensin-Aldosterone System

STUDY COMPENSATION:

Subjects will receive \$100 for their participation.

PUBLICATION OF RESEARCH:

It is anticipated that the observations made in this study will be presented at National meetings and will be submitted for publication in peer-reviewed journals, including those in the fields of Spinal Cord Medicine.

COST ANALYSIS:

Kessler Foundation will be not responsible for any costs associated with this project. This protocol will be funded by the NJ Commission on Spinal Cord Research (CSCR18FEL010).

REFERENCES:

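### Hypotheses 1B and 3C predict no association in low-level SCI and controls, but a correlation test at alpha 0.05 cannot show absence, and the associations are never compared between groups

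*Combined protocol and SAP*

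**What the plan says.** Two of the seven hypotheses predict a null, and each is set against a predicted association in high-level SCI.

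- **BP change and renin change.** 1A, for high-level SCI: "There will be an inverse relationship between the change in BP and change in plasma renin from supine rest to 60° HUT in individuals". 1B, for low-level SCI and controls: "There will be no relationship between the change in BP and change in plasma renin from supine rest to 60° HUT".
- **Renin change and supine PWV.** 3B: "Change in plasma renin during the HUT maneuver will be directly associated with supine PWV in individuals with high-level SCI". 3C: "There will be no relationship between the change in plasma renin during the HUT maneuver and supine PWV in persons with low-level SCI", and likewise in controls.

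The Statistical Analysis paragraph for each pair names a Pearson or Spearman correlation, an alpha of 0.05, and the two variables. For Aim 1: "The independent variable is change in SBP from supine rest to 60° HUT and the dependent variable is change in renin". For 3B/3C: "The independent variable is change in renin from supine rest to 60° HUT and the dependent variable is PWV during supine rest". Neither paragraph says whether the correlations are run by group, or whether low-level SCI and controls are pooled.

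The only between-group test in the plan belongs to 3A: "Differences in change in plasma renin during HUT between groups will be analyzed using univariate group by ANOVA". The only power statement belongs to that ANOVA as well.

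**The concern.** The scientific claim in each pair is that an association present in high-level SCI is absent elsewhere. As planned, the only possible support for 1B or 3C is a non-significant correlation in a small group. That result is expected when there is no association. It is also common when there is a moderate one.

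Nor does a significant result in one group and a non-significant result in another test whether the groups differ. The 3A ANOVA does not fill the gap, because it compares mean renin change and not the BP-renin or renin-PWV association.

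There is a further difficulty for 3B/3C. A correlation depends on the spread of the predictor, which here is renin change. 3A expects that renin "but will remain unchanged in individuals with low-level SCI and uninjured controls". That statement concerns means, but if the spread is also smaller in those groups, their r shrinks even when the slope is the same in every group. Lower correlations there could then reflect a narrow predictor range and not a different physiological relationship.

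**Working it through.** **Inputs from the documents.** 33 subjects: 22 with SCI and 11 controls (Research Design & Methodology, Subjects). Alpha is 0.05 (Data Analysis).

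**Assumptions.** The high/low split of the 22 is not stated; 11/11 is assumed and varied below. Sidedness is not stated; two-sided is assumed. Calculations use Pearson's r under normality. The true r values and SD ratios are illustrative, since the documents give none.

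**The plan's own figure.** No power or sample size is given for any correlation. The 3A power cannot be reproduced because no effect size is stated, and it does not bear on 1B or 3C.

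**1. What one group of 11 can show**

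- Critical r = t/√(n−2+t²) = 2.262/√(9+5.117) = 0.602. One-sided it is 0.521; at n=22 it is 0.423.
- The 95% CI half-width at r=0 is tanh(1.96/√8) = 0.600.
- Power at true r=0.5 is 0.364, so the miss rate is 0.636 in one comparison group and 0.636² = 0.404 in both.

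**2. How often the hypothesised pattern appears when the groups do not differ**

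The plan states no decision rule. The rule inferred here is: significant in high-level SCI, not significant elsewhere. Let p11 and p22 be the power at n=11 and n=22. The pattern probability is p11(1−p11)² if the comparison groups are analysed separately, and p11(1−p22) if they are pooled (which also assumes equal group means). At r=0.5 these are 0.364×0.636² = 0.147 and 0.364×0.312 = 0.114.

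| Same true r in all groups | 0.3 | 0.4 | 0.5 | 0.6 | 0.7 | 0.8 |
|---|---|---|---|---|---|---|
| Power, n=11 | 0.145 | 0.234 | 0.364 | 0.536 | 0.733 | 0.905 |
| Power, n=22 | 0.278 | 0.470 | 0.688 | 0.872 | 0.971 | 0.998 |
| Pattern, separate | 0.106 | 0.137 | 0.147 | 0.115 | 0.052 | 0.008 |
| Pattern, pooled | 0.105 | 0.124 | 0.114 | 0.069 | 0.021 | 0.002 |

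Other splits, groups analysed separately:

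- 8 high/14 low: 0.06–0.09 for r = 0.3–0.6, then about 0.02 and 0.002 at 0.7 and 0.8.
- 14 high/8 low: 0.14–0.22 for r = 0.3–0.6, then about 0.10 and 0.02.

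**3. Same slope, wider predictor spread in high-level SCI**

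With common slope r, residual SD √(1−r²) and predictor SD k times larger in high-level SCI, r_high = kr/√(k²r²+1−r²). For k=2 and r=0.4, r_high = 0.8/√(0.64+0.84) = 0.658. Power there is 0.649, and the pattern probability is 0.649×0.766² = 0.381.

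| Comparison-group r | 0.3 | 0.4 | 0.5 | 0.6 |
|---|---|---|---|---|
| Pattern, k=1.5 | 0.193 | 0.259 | 0.260 | 0.177 |
| Pattern, k=2 | 0.304 | 0.381 | 0.338 | about 0.20 |

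The plan gives a textual reason to consider unequal spread only for 3B/3C.

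**4. Whether equivalence could be shown**

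- At n=11 the 90% CI half-width at r=0 is tanh(1.645/√8) = 0.524, so the interval cannot lie inside ±0.5.
- For 80% power at true r=0, n = 3+[(1.645+1.282)/atanh(margin)]². A margin of 0.5 gives 31.4 (32 per group); a margin of 0.3 gives 92.4 (93 per group).

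**5. What a between-group contrast would deliver**

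The contrast is the high-level slope minus the mean of the other two slopes, with HC3 (heteroscedasticity-consistent) standard errors and t on 27 df. It was simulated with r in high-level SCI and 0 elsewhere.

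| r in high-level SCI | 0.3 | 0.4 | 0.5 | 0.6 | 0.7 | 0.8 |
|---|---|---|---|---|---|---|
| HC3 slopes, equal outcome SD | 8% | 12% | 18% | 26% | 37% | 52% |
| HC3 slopes, equal residual SD | 8% | 13% | 20% | 31% | 48% | 73% |
| Fisher z | 12% | 17% | 26% | 39% | 56% | 76% |

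If predictor SD is doubled in high-level SCI, HC3 power is 9–22% for r = 0.5–0.8 (equal outcome SD).

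Type I error with equal slopes:

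- HC3: 0.036–0.037 with equal spread, 0.031–0.033 with predictor SD ratios of 1.5 to 3, and 0.043–0.057 with residual SD ratios of 1.5 to 3.
- Ordinary least-squares errors: 0.08, 0.11 and 0.135 at residual SD ratios of 1.5, 2 and 3.
- Fisher z: 0.06–0.10, 0.10–0.21 and 0.24–0.53 at predictor SD ratios of 1.5, 2 and 3. It tests equal correlations, which is a different hypothesis from equal slopes.

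**The case against.** The plan never says that p>0.05 will be read as no relationship, so the pattern probabilities describe an inferred rule. That is true, and they should be read that way. The CI of ±0.60 and the 64% miss rate do not depend on the rule, although they do assume 11 per group.

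The SD ratios are speculative: the documents give no SD for renin change, BP change or PWV, and 3A speaks only of means. This also stands. The ratio figures show sensitivity and are not a forecast.

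The calculations are for Pearson's r, while the plan also allows Spearman's. The exact values would differ for Spearman, but a non-significant rank correlation in a group this small is no better evidence of absence.

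The strongest practical objection is that the added contrast has little power at N=33, so a non-significant contrast would also be inconclusive. That is correct. It is a reason to rely on estimates and intervals, and it gives no support to a null claim from the planned correlations.

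Finally, this is a small single-visit physiology study. However, the plan states directional and null hypotheses at alpha 0.05 and does not label these correlations exploratory.

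**Conclusion.** The concern holds. Nothing in the plan can support 1B or 3C as worded, or test whether the associations differ by group. That conclusion rests on the text and survives any split of the 22 and any pooling.

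The size depends on the assumptions. With 11 per group, a null-looking result is compatible with correlations up to about 0.60 in either direction. Under the inferred rule, identical true correlations of 0.3–0.6 in all groups would produce the hypothesised pattern in 11–15% of studies analysed separately, or 7–12% with the comparison groups pooled. At true correlations of 0.7–0.8 it is 5% or less in both cases. Equivalence at a margin of 0.5 is unattainable at this group size. This should be fixed before analysis, and confidence in the textual gap is high.

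**What to change.** 1. For each pair, report each group's correlation and slope with 95% CIs, and state that no relationship will not be concluded from p>0.05. If Spearman's coefficient is used, report it in the same way.
2. Reword 1B and 3C to predict an association weaker than in high-level SCI.
3. Add one exploratory group-by-predictor contrast of slopes per pair: high-level SCI against the mean of low-level SCI and controls, with HC3 standard errors. Report it as an estimate with a CI, and state that the two contrasts carry no confirmatory alpha. A Fisher-z contrast may be secondary, with a note that it can reject when slopes are equal but predictor spread differs.
4. State the high/low split of the 22, and whether low-level SCI and controls are analysed separately or pooled.

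The cost is SAP wording and one contrast per pair, using measurements the protocol already schedules. The downside is the low power shown above: a non-significant contrast will not establish that the groups are alike, and the write-up must say so.

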Hypothesis 3A: There will be significant group differences for change in plasma renin during HUT, in that plasma renin will be significantly increased during HUT in participants with high-level SCI, but will remain unchanged in individuals with low-level SCI and uninjured controls.

Hypothesis 3B: Change in plasma renin during the HUT maneuver will be directly associated with supine PWV in individuals with high-level SCI.

Hypothesis 3C: There will be no relationship between the change in plasma renin during the HUT maneuver and supine PWV in persons with low-level SCI and uninjured controls.

REVIEW OF LITERATURE:

After a SCI, descending sympathetic preganglionic neurons are disrupted causing loss of supraspinal regulation of cardiovascular function[1, 2],which results in numerous clinical issues. The level of the spinal lesion greatly influences the amount of cardiovascular regulation dysfunction after SCI. In individuals with injuries below T6, the sympathetic and parasympathetic control of the heart and splanchnic bed are intact, both of which are essential for short- and long- term BP regulation [2]. On the other hand, individuals with higher-level injuries, the parasympathetic control remains integral, while sympathetic autonomic control is lost (Krasnouk, 2009). This results in persistent hypotension and severe drops in BP when moving to the upright position (OH) [1, 3-7].

OH has a higher prevalence in individuals with cervical compared to individuals with thoracic lesions, irrespective of whether their lesion was complete or incomplete[8, 9]. According to a Consensus statement from the American Autonomic Society and American Academy of Neurology, OH is defined as a decrease in systolic BP (SBP) of 20+ mmHg and/or a fall in diastolic BP (DBP) of 10+ mmHg within 3-minutes of moving from supine to the upright position, with or without symptoms [10]. Interestingly, decreased plasma NE has been noted in individuals with cervical lesions when compared to individuals with thoracic injuries and controls [11-14]; and furthermore, there was no significant increase in NE level when individuals with tetraplegia underwent HUT [15, 16]. Additionally, lower levels of NE have been found to be associated with an increased incidence of OH in persons with SCI [17]. Individuals with

Orthostatic Blood Pressure and Arterial Stiffness in Persons with Spinal Cord Injury: The Effect of the Renin-Angiotensin-Aldosterone System

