lesions below the cervical spine have normal to high levels of plasma NE concentrations [13, 14] and, as a result, are less prone to hypotension and OH [3, 18, 19].

Additionally, OH after SCI is thought to be largely related to inability to centrally regulate vascular tone [20]. The loss of the reflex vasoconstriction of the splanchnic bed and lower extremity vasculature results in venous blood pooling, which results in reduced blood volume in end-diastolic volume, leading to a decrease in cardiac output and left ventricular stroke volume [21]. In addition, due to paralysis of the lower extremities and physical inactivity, persons with SCI lose their ability to use skeletal muscle pump by activating muscle contraction. Individuals with paraplegia and uninjured controls demonstrated increased total peripheral resistance during a head-up tilt (HUT) compared to cervical injuries [22]. This suggests that the SNS was increased in controls and individuals with low-level injuries because they were able to increase venous return in order to maintain BP.

Although many individuals with SCI demonstrate OH, symptoms associated with OH decrease over time (light-headedness, blurred vision, fatigue, weakness, etc.) [19]. Evidence demonstrates that increased dependency on the RAAS is believed to play an integral part in reducing the severity of postural hypotension and the associated symptoms [12, 16, 19, 23, 24]. Renin was shown to increase in individuals with tetraplegia during HUT, an orthostatic challenge, at a much quicker and higher rise compared to individuals with thoracic injuries and uninjured controls [12, 23, 25].

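### Hypotheses 1A/1B and 3B/3C are judged by a correlation coefficient whose size depends on the spread of the independent variable, so a smaller or non-significant r in low-level SCI and controls need not mean a weaker relationship

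*Combined protocol and SAP*

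**What the plan says.** In DATA ANALYSIS, the Statistical Analysis paragraphs for Aim 1 and for Hypotheses 3B/3C name one method: "we will use Pearson's correlation coefficient or Spearman's correlation coefficient with alpha", with alpha at 0.05. For 1A/1B, "The independent variable is change in SBP from supine rest to 60° HUT" and the dependent variable is change in renin. For 3B/3C, "The independent variable is change in renin from supine rest to 60° HUT and the dependent variable is PWV during supine rest".

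The hypotheses form a contrast. A relationship is expected in high-level SCI (1A, 3B). In low-level SCI and controls, 1B expects "There will be no relationship between the change in BP and change in plasma renin from supine rest to 60° HUT" and 3C expects "There will be no relationship between the change in plasma renin during the HUT maneuver and supine PWV". These paragraphs plan no slope, confidence interval, between-group comparison or margin for calling a relationship absent.

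Three statements bear on how much the independent variables may vary:
- REVIEW OF LITERATURE describes severe upright BP falls in higher-level injury.
- The same section says that people with lesions below the cervical spine "are less prone to hypotension and OH".
- Hypothesis 3A expects renin to rise in high-level SCI "but will remain unchanged in individuals with low-level SCI and uninjured controls".

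No SD or range is given for either change variable in any group.

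**The concern.** A correlation coefficient mixes two things: how much the outcome moves per unit of the independent variable, and how widely that variable is spread relative to the residual scatter. Aims 1 and 3 are about the first. If SBP change varies less in low-level SCI and controls, r will be smaller there and less often significant, even if each mmHg of fall goes with the same renin change in all three groups. The same applies to 3C if renin change varies less in those groups.

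At stake is what a result of significant in high-level SCI and non-significant elsewhere would mean. It could reflect a relationship specific to high-level SCI, or the same relationship seen over a narrower range. The planned output would not let a reader tell these apart. Spearman's coefficient is also reduced by a narrow range, so the stated alternative does not remove the problem.

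**Working it through.** **The plan's own figures.** None is given for these correlations. The only power figure (Hypothesis 3A, N = 33) is for the group ANOVA. It is printed unclearly and without an effect size, so it can be neither reproduced nor applied here.

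**Inputs from the documents.** 22 participants with SCI and 11 controls (RESEARCH DESIGN & METHODOLOGY, Subjects); alpha 0.05.

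**Assumptions.** SCI split 11/11; two-sided tests; low-level SCI and controls tested separately; r = -0.70 in high-level SCI; the same slope in all groups; normal data. Let k be the SD of SBP change in a comparison group divided by that in high-level SCI.

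**Attenuation.** In standardised units (high-level SD of SBP change = 1, slope magnitude 0.70, high-level residual variance 1 − 0.70² = 0.51):

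|r| = 0.70k / √(0.49k² + residual variance)

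At k = 0.5 the numerator is 0.35 and 0.49k² is 0.1225.
- Equal residual SD: 0.35/√(0.1225 + 0.51) = 0.44.
- Residual SD scaled by √k (variance 0.51 × 0.5 = 0.255): 0.35/√(0.1225 + 0.255) = 0.57.
- Residual SD scaled by k (variance 0.51 × 0.25 = 0.1275): 0.35/√(0.1225 + 0.1275) = 0.70, so no attenuation.

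**Significance threshold.** With n = 11, t(0.975, 9 df) = 2.262, and the critical |r| is 2.262/√(9 + 2.262²) = 0.602.

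**Chance of the 1A/1B pattern with identical slopes.** The groups are independent, so the rate is (power in high-level SCI) × (1 − power in a comparison group)². Power is simulated, with at least 40,000 studies per setting; it is 0.73 in high-level SCI.

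| Residual SD in comparison groups, k = 0.5 | \|r\| | Power | Pattern rate |
|---|---|---|---|
| Equal | 0.44 | 0.28 | 0.734 × 0.718² ≈ 38% |
| Scaled by √k | 0.57 | 0.48 | 0.734 × 0.52² ≈ 19–20% |
| Scaled by k | 0.70 | 0.73 | 0.734 × 0.266² ≈ 5% |

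The 5% is also the rate when all groups have equal spread. At k = 0.6, 0.4 and 0.3 the pattern rate is about 28%, 47% and 55% with equal residual SD; 15%, 26% and 33% with √k scaling; and 5% throughout with proportional scaling.

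**If the two comparison groups were pooled** (n = 22, critical |r| = 0.423), power at k = 0.5 with equal residual SD is 0.56 and the pattern rate is 0.734 × (1 − 0.559) ≈ 32%.

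**Would comparing the correlations cure it?** At k = 0.5 with identical slopes, a Fisher-z test of equal r rejects in about 12% of studies with equal residual SD, 7% with √k scaling and 5% with proportional scaling. A pooled-variance F test of equal slopes rejects in 5% with equal residual SD, but in only about 3% with proportional scaling. The slope comparison should therefore allow unequal residual variance.

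**What slopes would show** (equal residual SD). The 95% CI half-width for a comparison-group slope is about 2.262 × √0.51 / (k√10): 0.51 at k = 1 and 1.02 at k = 0.5, against a high-level slope of 0.70. If the comparison slopes are truly zero, the slope-by-group test has power of about 0.52 at k = 1, 0.29 at k = 0.5 and 0.18 at k = 1/3.

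**The case against.** The strongest reply is that narrow spread is not in the documents. Being less prone to OH describes how often a threshold fall occurs, and that sentence does not mention controls. Renin remaining unchanged is a prediction about group response; a mean change near zero can go with wide individual variation. This stands. A reader might infer that the protocol itself predicts narrow spread and so builds in the contrast, but the text does not support that. The inference is plausible for 3C and indirect for 1B.

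Second, renin change is the dependent variable in 1A/1B and the independent variable in 3B/3C. If it varies little in the comparison groups, as the 3C argument supposes, residual scatter in 1B should be smaller too. The equal-residual setting leaves the SD of renin change at √(0.1225 + 0.51) ≈ 80% of the high-level value. This also stands, and is why 38% cannot be quoted without the 19–20% and 5%.

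Third, within a group the test of Pearson's r and the test of the slope against zero have the same p-value. A reader might take the pattern rate as the price of choosing r; it mostly reflects treating non-significance as absence. What is specific to r is that its size is not comparable across groups with different spread.

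Two further inferences go too far. One is that the mechanistic conclusion would be reversed: with equal slopes, larger falls would still produce more renin release in high-level SCI, which 3A tests directly. The other is that the figures carry over to 3B/3C: they are for SBP change only, and for PWV only the mechanism carries over.

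None of this makes r, or a pair of p-values, a sound basis for saying that a relationship exists in one group and not in another.

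**Conclusion.** The point holds conditionally. As planned, a smaller or non-significant correlation in low-level SCI or controls would not distinguish a weaker relationship from a narrower range of the independent variable. The artefact requires both a narrower spread in those groups and residual scatter that does not shrink in proportion; the documents settle neither. At half the spread, its size runs from none (5%, the equal-spread rate) through 19–20% to about 38%. These rates rest on the assumed r = -0.70, the 11/11 split, two-sided alpha and separate tests. The plan should be changed because the wording allows an unsupported finding of no relationship and the remedy uses data already being collected.

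**What to change.** In the Aim 1 and Aim 3 (3B/3C) Statistical Analysis paragraphs:
- Report the regression slope with its 95% CI for each group: renin change per mmHg of SBP change, and PWV per unit of renin change.
- Next to each slope, give the SD and range of the independent variable in that group.
- Base any claim that the relationship differs between groups on a slope-by-group comparison that allows unequal residual variance, not on r or on one p-value being significant and another not.
- Report 1B and 3C as unresolved when the interval is wide, for example when it includes both zero and the high-level slope estimate.
- Keep Pearson and Spearman as descriptive, with Spearman as a check for skew and outliers, which matter for a linear slope at this group size.

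The cost is wording; no new data are needed. The downside is low power for the slope comparison at N = 33 (about 0.3 at half spread if the comparison slopes are truly zero), so 1B and 3C will often be inconclusive.

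### Hypothesis 2A names neither a sign nor a group, and its unadjusted correlation, if run on all 33 subjects, can be significant through lesion level alone

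*Combined protocol and SAP*

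**What the plan says.** Hypothesis 2A appears under Specific Aims and again under Data Analysis, Aim 2: "There will be a linear relationship between the change in orthostatic BP and change in plasma NE concentration from supine rest to 60° HUT". The Aim 2 statistical paragraph says: "To determine the relationship between change in BP and NE, we will use Pearson's correlation coefficient or Spearman's correlation coefficient with alpha". It then defines the variables: "The independent variable is change in SBP from supine rest to 60° HUT and the dependent variable is change in NE", measured over the same interval, with alpha 0.05. It mentions no group, no adjustment, no sidedness, no rule for choosing between the two coefficients, and no statement on whether groups are combined.

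The other hypotheses that predict an association give both a direction and a population:
- 1A, for the high-level injury group only: "There will be an inverse relationship between the change in BP and change in plasma renin from supine rest to 60° HUT in individuals".
- 2B: "Plasma renin activity will be inversely related to plasma NE concentrations during HUT in persons with SCI".
- 3B: change in renin "will be directly associated with supine PWV in individuals with high-level SCI".

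Hypotheses 1B and 3C predict no relation, and each names its groups.

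The Review of Literature describes how the groups should differ. It describes severe BP drops on standing in higher-level injury and reports that "there was no significant increase in NE level when individuals with tetraplegia underwent HUT". Lower lesions are said to have normal to high NE and to be less prone to OH. On the peripheral resistance response to tilt it concludes: "This suggests that the SNS was increased in controls and individuals with low-level injuries".

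**The concern.** There are two gaps, and they compound each other.

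First, with no sign stated, a significant coefficient in either direction fits the wording of 2A. The two directions mean different things. A positive r says that those whose SBP falls most release least NE; a negative r says that those whose SBP falls most release most.

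Second, with no group stated, the correlation is most naturally run on all 33 subjects. The protocol recruits groups that its own background expects to differ on both variables. When groups are separated on both axes, a pooled correlation mixes the difference between groups with any relation inside them. 2A could then be declared confirmed when SBP change and NE change are unrelated among people of the same lesion level. The result would restate a group contrast that the literature review already reports, and would say nothing about how one person's BP response relates to their NE response.

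**Working it through.** **Plan's own figure.** The document gives no sample size, power or effect size for 2A. Its only power statement belongs to Hypothesis 3A, so there is nothing to reproduce here.

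**Inputs from the document.** 22 subjects with SCI and 11 controls, 33 in total; SCI strata C1-T1 and T6-T12; x = change in SBP and y = change in NE, supine to 60°; alpha 0.05.

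**Assumptions.** An 11/11 split of the SCI subjects; a two-sided test; Pearson's r; unit within-group SDs on both variables; low-level SCI and controls with equal means; the high-level group shifted by −d SDs on both axes (larger SBP fall, smaller NE rise). The document gives neither d nor the within-group correlation ρ, so a range is shown.

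**Critical values.** r_crit = t / √(t² + n − 2).
- n = 33: t(31) = 2.040, so r_crit = 2.040 / √(4.160 + 31) = 0.344.
- n = 11: t(9) = 2.262, so r_crit = 2.262 / √(5.117 + 9) = 0.602.

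Pooling or not therefore changes what the test can detect: 80% power needs |r| of about 0.47 at n = 33 and about 0.76 at n = 11.

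**Pooled correlation.** One third of the sample is shifted by d on both axes, so the between-group variance of each variable, and their between-group covariance, is (1/3)(2/3)d² = 2d²/9. Hence

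r_pooled = (ρ + 2d²/9) / (1 + 2d²/9).

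With no relation inside any group (ρ = 0):
- d = 1: 0.222 / 1.222 = 0.18
- d = 1.5: 0.500 / 1.500 = 0.33
- d = 2: 0.889 / 1.889 = 0.47

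**Simulation of the same setting (3 × 11, ρ = 0).** The adjusted slope is the common within-group slope, with 33 − 3 − 1 = 29 error df.

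| d (SD) | mean pooled r | pooled test significant | group-adjusted slope significant |
|---|---|---|---|
| 0 | 0.00 | 5% | 5% |
| 1 | +0.19 | about 17% | 5% |
| 1.5 | +0.34 | about 51% | 5% |
| 2 | +0.48 | about 87% | 5% |

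Repeat runs agree to within about one percentage point.

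**Opposite case, as a conditional only.** If the relation were negative inside every group, the pooled r would be zero where ρ = −2d²/9, that is d = √(4.5|ρ|): 1.16 SD for ρ = −0.3, 1.50 for −0.5 and 1.77 for −0.7. If the high-level group were flat and the other two had ρ = −0.5, the average within-group covariance would be −1/3 and the zero would fall at d = √(4.5/3) = 1.22.

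**Common slope when slopes differ.** With the high-level group flat and the other two at ρ = −0.5, a common group-adjusted slope is significant in only about 46% of trials, because it averages unlike slopes. With −0.5 in all three groups it is 84%.

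**The case against.** *The text never says pooled.* True. The Aim 1 and 3B/3C paragraphs use the same group-free wording for hypotheses that are explicitly group-specific, so that wording does not establish pooling. But for those aims the hypothesis supplies the group. For 2A nothing does, so all 33 is the natural reading, though not a certain one. If separate groups were intended, the plan has to say so, because the detectable correlation changes greatly.

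*A non-directional hypothesis tested two-sided is legitimate, and the sign of r will be visible.* This stands. The missing sign is a weakness of specification and does not make the test invalid. The document does not make 2A primary.

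*A stronger reading that the document does not support.* A reader might infer that the protocol's own account implies opposite signs between and within groups, so that the correlation cancels to zero while every group has a real relation. Nowhere does the document say that a larger SBP fall goes with a larger NE rise inside any group; that would be outside physiology. Its one statement closest to a relation among patients, that lower NE goes with more OH in SCI, points to a positive sign. A real relation in every group also sits badly with the absence of an NE rise reported in tetraplegia. And near-zero pooled values occur only around particular d: with ρ = −0.5 throughout, the pooled r averages −0.41 at d = 0.5 and +0.39 at d = 2.5.

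**Conclusion.** The point holds in a limited form. 2A lacks a sign, a population and a pooled-or-per-group rule, and the Aim 2 analysis supplies none of them. Read naturally, as one unadjusted correlation over 33 subjects, the test can be significant because of lesion level alone: in about 17%, 51% and 87% of trials at shifts of 1, 1.5 and 2 SD, where a group-adjusted slope stays at 5%. The direction of the shift comes from the protocol's background. Its size, the zero within-group correlation, the 11/11/11 split and the use of Pearson's r are assumptions.

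Cancellation of a negative within-group relation is arithmetically possible, but only under assumptions that the document does not make. It should not be presented as a consequence of the protocol. This is a cheap improvement to a secondary-type analysis, and it does not show that the study's design is unsound.

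**What to change.** 1. The sponsor states, in Hypothesis 2A, the expected sign and the population to which it applies. Both are the sponsor's choice.
2. Replace the unadjusted correlation as the test of 2A with a regression of NE change on SBP change with group (high-level SCI, low-level SCI, control) as a factor.
3. Report the slope and 95% CI for each group. If slopes are expected to differ, for example flat in high-level SCI, add an SBP-change-by-group term and base the conclusion on the group-specific slopes, since a common slope would average them.
4. Present the pooled r, with a scatter plot marked by group, as description only.

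Cost: one hypothesis and one analysis sentence reworded, and no new data. Group as a factor takes two degrees of freedom (error df 31 to 29); the interaction takes two more (27). Group-specific slopes will be imprecise at about 11 per group: power is only about 0.34 for a within-group correlation of 0.5. They should be read through their intervals and not by significance alone.
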